7.6.3. Donor Chimerism

Donor chimerism after a hematopoietic stem cell transplant involves identifying the genetic profiles of the recipient and of the donor and then evaluating the ratio of donor to recipient cells in the recipient's blood, bone marrow, or other tissue. Chimerism testing using peripheral blood or bone marrow will be performed at the treating investigator's discretion according to local institutional practice as indicated in Table 5. In general, genomic polymorphisms should be assessed via polymerase chain reaction analysis of short tandem repeat loci from isolated lymphocytes or myeloid cells. Fluorescence *in situ* hybridization analysis may also be used in cases with sex-mismatched transplants (Matsuda et al 2004).

7.6.4. Post-Transplant Lymphoproliferative Disorder Assessment

Staining for Epstein-Barr virus for PTLD testing will be performed according to local institutional practice at the treating investigator's discretion as indicated in Table 5.

7.7. Pharmacokinetic Assessments

7.7.1. Blood Sample Collection

Pharmacokinetic samples will be obtained on Days 1, 7, and 14. On each of these days, a predose blood sample will be drawn, study treatment will be administered, and serial blood samples will be taken at the intervals shown in Table 9.

The exact date and time of the PK blood draws will be recorded in the eCRF along with the date and time of the last dose of study drug preceding the blood draw (if applicable) and the time of the most recent meal. Instructions for sample preparation and shipping will be provided in the Laboratory Manual. Subjects will receive reminder cards in advance of the study visit providing instruction to hold the dose of study drug on the day of the visit, as well as a place to record the time of the previous dose of study drug and time of the most recent meal or snack consumed.

If PK samples are missing for a subject, PK sample collection should be performed at the next visit. On Days 1, 7, and 14, subjects must refrain from taking study medication before arriving for the visit. Subjects should not have consumed any food within 8 hours before arriving at the clinic. A trough (predose) PK sample (30-minute window) should be drawn at each of the PK visits. Following the trough PK sample, the subject should take the assigned dose of study treatment, and subsequent timed samples will be taken. Food should be withheld until 1 hour after study drug administration.

Study Day	Timing of Sample Relative to INCB018424 Administration								
Day 1	Predose	1 h ± 15 min	2 h ± 30 min	4-8 h					
Day 7	Predose	1 h ± 15 min	2 h ± 30 min	4-8 h					
Day 14	Predose	1 h ± 15 min	2 h ± 30 min	4-8 h					

 Table 9:
 Pharmacokinetic Sample Collection Time and Windows

7.7.2. Bioanalytical Methodology and Analysis

Plasma samples will be analyzed for ruxolitinib by a validated liquid chromatography-tandem mass spectrometry assay. These samples will be analyzed by Incyte Corporation (Wilmington, DE) or its designee.

Pharmacokinetic parameters will be calculated from the plasma concentrations of ruxolitinib according to a model-independent approach or population PK approach. Instructions regarding sample collection, handling, and shipping will be provided in the Laboratory Manual.

7.9. Other Study Procedures

7.9.1. Distribution of Subject Reminder Cards

Subjects will be provided with a reminder card at each visit. The subject reminder card will indicate the date/time of the next visit and will also remind the subject to not take the study drug on Days 1, 7, and 14 until after blood samples for PK and safety have been drawn in the clinic. The reminder cards for the Day 1, 7, and 14 visits will have an area for the subject to record the date and time of the last dose taken (from the previous day) and the time of their last meal before the visit.

8. SAFETY MONITORING AND REPORTING

8.1. Adverse Events

8.1.1. Definitions

For the purposes of this Protocol, an adverse event (AE) is defined as any untoward medical occurrence associated with the use of a drug in humans, whether or not considered drug related that occurs after a subject provides informed consent. Abnormal laboratory values or test results occurring after informed consent constitute AEs only if they induce clinical signs or symptoms, are considered clinically meaningful, require therapy (eg, hematologic abnormality that requires transfusion), or require changes in the study drug(s).

8.1.2. Reporting

Adverse events that begin or worsen after informed consent should be recorded on the Adverse Events form of the eCRF. Conditions that were already present at the time of informed consent should be recorded on the Medical History form in the eCRF. Monitoring for the occurrence of new AEs should be continued for at least 30 days after the last dose of study drug. Adverse events (including laboratory abnormalities that constitute AEs) should be described using a diagnosis whenever possible rather than by individual underlying signs and symptoms. When a clear diagnosis cannot be identified, each sign or symptom should be reported as a separate AE.

The term "disease progression" should be recorded as an AE/SAE itself only if there are no other identifiable AEs/SAEs associated with the disease progression at the time of reporting. For events associated with disease progression, the relevant signs and symptoms should be reported using a diagnosis whenever possible rather than individual underlying signs and symptoms. When a clear diagnosis cannot be identified, each sign or symptom should be reported as a separate AE. If the events resulting from disease progression meet the criteria for an SAE (eg, resulted in hospitalization, a life-threatening event, or death), the specific event(s) should be reported as an SAE(s) as described in Section 8.3.2. In both cases (ie, AEs or SAEs related to disease progression), for each event it should be indicated whether the event (diagnosis or signs and symptoms) is related to disease progression.

The severity of AEs will be assessed using CTCAE v4.03 Grades 1 through 4. The CTCAE v4.03 severity of Grade 5 will not be used; AEs resulting in death will be graded accordingly using Grades 1 through 4 and have the outcome noted as fatal. If an event is not classified by CTCAE, the severity of the AE will be graded according to the scale below to estimate the grade of severity:

Grade 1	Mild; asymptomatic or mild symptoms; clinical or diagnostic observations only; intervention not indicated.
Grade 2	Moderate; minimally, local, or noninvasive intervention indicated; limiting age-appropriate activities of daily living.
Grade 3	Severe or medically significant but not immediately life-threatening; hospitalization or prolongation of hospitalization indicated; disabling; limiting self-care activities of daily living.
Grade 4	Life-threatening consequences; urgent intervention indicated.

The occurrence of AEs should be sought by nondirective questioning of the subject during the screening process after signing the ICF and at each visit during the study. Adverse events may also be detected when they are volunteered by the subject during the screening process or between visits, or through physical examination, laboratory test, or other assessments. To the extent possible, each AE should be evaluated to determine:

- The severity grade (CTCAE Grade 1 to 4).
- Whether there is at least a reasonable possibility that the AE is related to the study treatment: suspected (yes) or not suspected (no).
- The start and end dates, unless unresolved at final follow-up.
- The action taken with regard to study drug.
- The event outcome (eg, not recovered/not resolved, recovered/resolved, recovering/resolving, recovered/resolved with sequelae, fatal, unknown).
- The seriousness, as per serious adverse event (SAE) definition provided in Section 8.3.1.

Unlike routine safety assessments, SAEs are monitored continuously and have special reporting requirements (see Section 8.3.2).

All AEs should be treated appropriately. If an AE is treated with a concomitant medication or nondrug therapy, this action should be recorded on Adverse Event form and the treatment should

be specified on the Prior/Concomitant Medications or Procedures and Non-Drug Therapy form in the eCRF.

Once an AE is detected, it should be followed until it has resolved or until it is judged to be permanent; assessment should be made at each visit (or more frequently if necessary) of any changes in severity, the suspected relationship to the study drug, the interventions required to treat the event, and the outcome.

When the severity of an AE changes over time for a reporting period (eg, between visits), each change in severity will be reported as a separate AE until the event resolves. For example, 2 separate AEs will be reported if a subject has Grade 1 diarrhea, meeting the definition of an AE, which lasts for 3 days before worsening to a Grade 3 severity. The Grade 1 event will be reported as an AE with a start date equal to the day the event met the Grade 1 AE definition and a stop date equal to the day that the event increased in severity from Grade 1 to Grade 3. The Grade 3 event will also be reported as an AE, with the start date equal to the day the event changed in intensity from Grade 1 to Grade 3 and a stop date equal to the day that the event either changed severity again or resolved. For analysis purposes, this will be considered 1 AE for this subject, and the highest reported severity will be used.

8.2. Laboratory Test Abnormalities

Laboratory abnormalities that constitute an AE in their own right (considered clinically meaningful, induce clinical signs or symptoms, require concomitant therapy, or require changes in study drug) should be recorded on the Adverse Event form in the eCRF. Whenever possible, a diagnosis rather than a symptom should be provided (eg, "anemia" instead of "low hemoglobin"). Laboratory abnormalities that meet the criteria for AEs should be followed until they have returned to normal or an adequate explanation of the abnormality is found. When an abnormal laboratory test result corresponds to a sign or symptom of a previously reported AE, it is not necessary to separately record the laboratory test result as an additional event.

Laboratory abnormalities that do not meet the definition of an AE should not be reported as AEs. A Grade 3 or 4 (severe) AE does not automatically indicate an SAE unless it meets the definition of serious, as defined in Section 8.3.1, and/or per the investigator's discretion. A dose modification for the laboratory abnormality may be required (see Section 5.4.2) and should not contribute to the designation of a laboratory test abnormality as an SAE.

8.3. Serious Adverse Events

8.3.1. Definitions

An SAE is defined as an event that meets at least 1 of the following criteria:

- Is fatal or life-threatening.
- Requires inpatient hospitalization or prolongation of existing hospitalization, unless hospitalization is a result of:
 - A routine treatment or monitoring of the studied indication not associated with any deterioration in condition.

- An elective surgery or preplanned treatment for a pre-existing condition that is unrelated to the indication under study and has not worsened since signing the ICF.
- A treatment on an emergency outpatient basis for an event not fulfilling any of the definitions of a SAE and not resulting in hospital admission.
- Any social reasons and respite care, in the absence of any deterioration in the subject's general condition.
- Results in persistent or significant disability, incapacity, or a substantial disruption of a person's ability to conduct normal life functions.
- Constitutes a congenital anomaly or birth defect.
- Is considered to be an important medical event or a medically significant event that may not result in death, be immediately life-threatening, or require hospitalization but may be considered serious when, based upon appropriate medical judgment, the event may jeopardize the subject or may require medical or surgical intervention to prevent 1 of the outcomes listed above.

8.3.2. Reporting

Every SAE, regardless of suspected causality (eg, relationship to study drug(s) or study procedure or disease progression), occurring after the subject has signed the ICF through the last study visit (or 30 days) after the last dose of study drug, whichever is later) must be reported to the sponsor (or designee) within **24 hours** of learning of its occurrence, unless otherwise specified by the Protocol. Any SAEs occurring more than 30 days after the last dose of study drug should be reported to the sponsor or its designee only if the investigator suspects a causal relationship to the study drug.

Information about all SAEs is collected and recorded on the Adverse Event form of the eCRF. The investigator must assess and record the causal relationship of each SAE to each specific study drug (ruxolitinib and corticosteroids) during the time it is given.

The investigator must also complete the Incyte Serious Adverse Event Report Form, in English, and send the completed and signed form to the sponsor or designee within 24 hours of becoming aware of the SAE. The investigator must provide a causality assessment, that is, assess whether there is at least a reasonable possibility that the SAE is related to the study treatment: suspected (yes) or not suspected (no). Refer to the Incyte Reference Guide for Completing the Serious Adverse Event Report Form.

The contact information of the sponsor's study-specific representatives is listed in the investigator manual provided to each site. The original copy of the SAE Report Form and the confirmation sheet must be kept at the study site.

Investigational site personnel must report any new information regarding the SAE within 24 hours of becoming aware of the information in the same manner that the initial SAE Report Form was sent. Follow-up information is recorded on an amended or new SAE Report Form, with an indication that it is follow-up to the previously reported SAE and the date of the original report. The follow-up report should include information that was not provided on the previous

SAE Report Form, such as the outcome of the event (eg, resolved or ongoing), treatment provided, action taken with study drug because of the SAE (eg, dose reduced, interrupted, or discontinued), or subject disposition (eg, continued or withdrew from study participation). Each recurrence, complication, or progression of the original event should be reported as follow-up to that event, regardless of when it occurs.

If the SAE is not documented in the IB for the study drug (new occurrence) and is thought to be related to the sponsor's study drug, the sponsor or its designee may urgently require further information from the investigator for reporting to health authorities. The sponsor or its designee may need to issue an Investigator Notification (IN) to inform all investigators involved in any study with the same drug that this SAE has been reported. Suspected Unexpected Serious Adverse Reactions (SUSARs) will be collected and reported to the competent authorities and relevant ethics committees in accordance with Directive 2001/20/EC, or as per national regulatory requirements in participating countries.

8.4. Emergency Unblinding of Treatment Assignment

Not applicable.

8.5. Pregnancy

Pregnancy, in and of itself, is not regarded as an AE unless there is suspicion that study drug may have interfered with the effectiveness of a contraceptive medication or method. When a pregnancy has been confirmed in a subject during maternal or paternal exposure to study drug, the following procedures should be following in order to ensure subject safety:

- The study drug must be discontinued immediately (female subjects only; see Section 5.4.1 for the maximum permitted duration of study drug interruption).
- The investigator must complete and submit the Incyte Clinical Trial Pregnancy form to the sponsor or its designee within **24 hours** of learning of the pregnancy.

Data on fetal outcome and breastfeeding are collected for regulatory reporting and drug safety evaluation. Follow-up should be conducted for each pregnancy to determine outcome, including spontaneous or voluntary termination, details of the birth, and the presence or absence of any birth defects, congenital abnormalities, or maternal and/or newborn complications, by following until the first well-baby visit. Pregnancy should be recorded on a Clinical Trial Pregnancy form and reported by the investigator to the sponsor or its designee. Pregnancy follow-up information should be recorded on the same form and should include an assessment of the possible causal relationship to the sponsor's study drug to any pregnancy outcome, as well as follow-up to the first well-baby visit or the duration specified in local regulations, whichever is later. Refer to the Incyte Reference Guide for Completing the Clinical Trial Pregnancy Form.

Any SAE occurring during pregnancy must be recorded on the SAE report form and submitted to the sponsor or designee.

8.6. Warnings and Precautions

Special warnings or precautions for the study drug, derived from safety information collected by the sponsor or its designee, are presented in the Investigator's Brochure (IB). Additional safety information collected between IB updates will be communicated in the form of Investigator Notifications (INs). Any important new safety information should be discussed with the subject during the study, as necessary. If new significant risks are identified, they will be added to the ICF.

8.7. Data Monitoring Committee

There is no formal Data Monitoring Committee review.

The sponsor will continuously monitor safety through frequent contact with the treating investigators, review of the clinical data, and formal study meetings. Routine teleconferences will be held among participating study sites to provide subject-by-subject updates on current study status, interim toxicities reported, and any other pertinent information. Adverse event and laboratory data entered into the clinical database will be reviewed periodically for trends and evolving safety signals.

8.8. Product Complaints

The sponsor collects product complaints on study drugs and drug delivery systems used in clinical studies in order to ensure the safety of study participants, monitor quality, and facilitate process and product improvements.

All product complaints associated with material packaged, labeled, and released by the sponsor or its designee will be reported to the sponsor. All product complaints associated with other study material will be reported directly to the respective manufacturer.

The investigator or his/her designee is responsible for reporting a complete description of the product complaint via email or other written communication to the sponsor contact or respective manufacturer as noted in the packaging information. Any AE associated with a product complaint should be reported as described in Section 8.1.2 of this Protocol.

If the investigator is asked to return the product for investigation, he/she will return a copy of the product complaint communication with the product.

9. STATISTICS

9.1. Study Populations

Subject enrollment, disposition, demographics, and medical history will be summarized at baseline. Dose exposure will be calculated for each subject. Safety and disease response data will be compared over time to assess change from baseline, during treatment, and follow-up.

The populations to be analyzed include the following:

- Efficacy Evaluable Population: Subjects enrolled into the study.
- Safety Evaluable Population: Subjects enrolled into the study who received at least 1 dose of study drug.
- Pharmacokinetic Evaluable Population: Subjects who receive at least 1 dose of study drug and provide at least 1 plasma sample (1 PK measurement) after study drug administration will be considered as potential PK evaluable subjects. The study pharmacokineticist will review data listings of study drug administration and sample records to identify subjects to be excluded from analyses of PK data.

9.2. Selection of Sample Size

Approximately 70 subjects are planned for the final analysis of the primary endpoint of ORR. A treatment regimen for steroid-refractory GVHD demonstrating an absolute improvement of 20% versus historic data would be considered clinically meaningful. With the assumed true rate of 60%, a sample size of 70 subjects would provide > 90% probability to have a 95% CI with lower limit of \geq 40%.

An interim analysis will be conducted when 35 subjects complete the Day 28 visit in order to assess for futility; if the lower boundary is crossed, the study will be terminated.

A group sequential design method for 1 sample binary outcome data will be used to calculate the lower boundary of futility. The spending function of HSD(-4) will be used. For H0: p = 0.4, Ha: p = 0.6, and a 1-sided binomial test with alpha of 0.025, if ≤ 15 subjects respond at the time of the interim analysis, the study will be terminated. This will provide 70.03% probability for the response rate of 40% at the interim analysis.

If \geq 37 subjects respond at the time of final analysis, the study outcome will be considered positive. These assumptions will provide 89.88% power for the response rate of 60% in the final analysis with Type I error of 0.0189.

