9.3. Level of Significance

No formal statistical tests will be performed. All CIs will be 95%.

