3.1. Control of Type I Error

No formal statistical tests will be performed. All confidence intervals (CIs) will be 95%.

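### The >90% probability ignores the futility stop (89.88% with it), and the plan both disclaims and specifies a formal test, with two success criteria that agree at 69 and 70 subjects but part at 68, 71 and 72

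*Protocol*

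**What the plan says.** Protocol 9.2 opens with "Approximately 70 subjects are planned for the final analysis of the primary endpoint of ORR" and continues "With the assumed true rate of 60%, a sample size of 70 subjects would provide > 90% probability" that the lower 95% limit is 40% or more. It then adds an interim look: "An interim analysis will be conducted when 35 subjects complete the Day 28 visit in order to assess for futility". The study stops if no more than "15 subjects respond at the time of the interim analysis, the study will be terminated". The design basis is "For H0: p = 0.4, Ha: p = 0.6, and a 1-sided binomial test with alpha of 0.025", and 37 or more responders at the end makes the study positive. The section closes with "These assumptions will provide 89.88% power for the response rate of 60% in the final analysis with Type I error of 0.0189". SAP 3.2 repeats all of this. Protocol 9.6 and SAP 9 repeat the interim rule, hypotheses, count and error rates.

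The synopsis (Statistical Methods) gives the >90% figure and then mentions the futility stop. It gives neither 89.88% nor the count of 37.

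On testing, Protocol 9.3 says "No formal statistical tests will be performed. All CIs will be 95"%. SAP 3.1, headed as control of type I error, says "No formal statistical tests will be performed. All confidence intervals (CIs) will be 95"%. SAP 7.2, headed as efficacy hypotheses, repeats the disclaimer. The primary analysis sections (Protocol 9.4.1, SAP 7.3.1) promise an estimate with a 95% CI, which the SAP specifies as exact binomial. Neither mentions the count of 37 or any other success criterion.

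**The concern.** There are two issues. First, one section gives two probabilities for what turns out to be the same event and does not say that the first ignores the interim. Someone who reads only the synopsis sees the higher figure beside a stopping rule under which it does not apply.

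Second, hypotheses, an alpha, a rejection count and a declared outcome together make a test, yet the sections that should define error control say there is none. This is a single-arm trial whose conclusion rests on one threshold. A reader cannot tell whether that threshold is a prespecified criterion or a benchmark, nor whether the count or the CI governs if the two disagree. With enrolment only approximately 70, no replacement of subjects (Protocol 4.3.2) and an efficacy population of everyone enrolled (Protocol 9.1, SAP 5.3.1), the final denominator need not be 70.

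**Working it through.** **Inputs.** p0 = 0.40, p1 = 0.60, 1-sided alpha 0.025; N = 70; interim at 35 with a stop at 15 or fewer; success at 37 or more (all Protocol 9.2). Exact 95% CI (SAP 7.3.1).

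**Formulas.** Exact lower limit for x of n: LL(x, n) = the 2.5% quantile of Beta(x, n − x + 1). Probability of success with the stop: S(p; n, r) = Σ over x = 16 to 35 of P[Bin(35, p) = x] × P[Bin(n − 35, p) ≥ r − x].

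**The plan's own figures.**
- P[Bin(35, 0.40) ≤ 15] = 0.7003 (stated 70.03%).
- S(0.60; 70, 37) = 0.8988 (stated 89.88%).
- S(0.40; 70, 37) = 0.0189 (stated 0.0189).

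All three reproduce.

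**The two criteria at n = 70.** LL(36, 70) = 39.17% and LL(37, 70) = 40.55%. A lower limit of at least 40% is therefore the same event as 37 or more responders. Wilson and Wald limits also first reach 40% at 37.

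**The >90% figure.** With no interim, P[Bin(70, 0.60) ≥ 37] = 0.9094, so >90% is right for a fixed sample. With the stop it is 0.8988.
- Loss from the stop: 90.94 − 89.88 = 1.06 points.
- Shortfall below 90%: 90 − 89.88 = 0.12 points.
- Chance of stopping when the true rate is 60%: P[Bin(35, 0.60) ≤ 15] = 3.00%.

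With no interim, the type I error of the 37 rule at n = 70 is 0.0199.

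**Near n = 70.** The same formulas, keeping the stop at 15 of 35:

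| n | LL at 36 | LL at 37 | Smallest count with LL ≥ 40% | Type I error of ≥37, with stop (without) | Probability of LL ≥ 40% at p = 0.60, with stop |
|---|---|---|---|---|---|
| 68 | 40.45% | 41.88% | 36 | 0.0110 (0.0113) | 89.5% |
| 69 | 39.80% | 41.20% | 37 | 0.0145 (0.0151) | 87.7% |
| 70 | 39.17% | 40.55% | 37 | 0.0189 (0.0199) | 89.9% |
| 71 | 38.56% | 39.92% | 38 | 0.0241 (0.0258) | 88.2% |
| 72 | 37.98% | 39.31% | 38 | 0.0303 (0.0330) | 90.3% |

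- At 68, 36 responders pass the CI and fail the count.
- At 71, 37 responders pass the count and fail the CI, although the count rule with the stop still has a type I error below 0.025.
- At 72, the count rule exceeds 0.025 even with the stop.

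**The case against.** The strongest reply is that the plan's numbers are all correct. The >90% sentence describes a sample of 70, comes before the interim is introduced and is true as a fixed-sample statement. The plan never calls it power. The figure it does call power is 89.88%, printed in the same section and in three others. A gap of 0.12 points changes neither the sample size nor the boundary nor the count, and moving enrolment by one or two subjects shifts the probability by more than that. All of this stands. A reader might infer that >90% is a miscalculation or that the power claim is false. The documents do not support that: it is a correct figure without a label, and only the synopsis omits its counterpart.

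On testing, the reply is that a design can be calibrated with hypotheses and a success count and then reported by a CI, and that at n = 70 the two give one decision. That is also right. It would be too strong to say that a trial disclaiming tests cannot define a positive result, or that type I error is uncontrolled as planned: at 70 it is 0.0189, and 0.0199 if the stop is not followed. What the reply does not meet is that the equivalence is never stated and fails at 68, 71 and 72, all within what approximately 70 allows. It is also fair that declaring a test is a substantive choice for the sponsor; but the current text already makes both choices.

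**Conclusion.** The point holds in two parts of unequal weight.

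The lesser part is labelling: under the design as written the probability is 89.88%, not above 90%, and the synopsis should say so. This rests on the stop being mandatory, as its wording indicates.

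The greater part is a contradiction in current text about whether a test is performed, together with silence on which criterion governs. At exactly 70 subjects it has no effect on the decision. One subject more, or two either way, is enough for the count and the exact CI to disagree at a borderline result, and at 72 the fixed count takes the type I error to 0.0303 against a nominal 0.025. These figures assume that the interim stays at 15 of 35 and that the denominator is everyone enrolled. How far enrolment would depart from 70 is not given; the range 68 to 72 is illustrative. The plan should be corrected before the primary data are read, but neither the sample size nor the stopping boundary needs to change.

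**What to change.** 1. In the synopsis, Protocol 9.2 and SAP 3.2, restate the probability as: *about 89.9%, allowing for the futility stop (90.9% ignoring it)*.
2. In Protocol 9.3 and SAP 3.1 and 7.2, replace the disclaimer with: *One primary hypothesis is evaluated: H0 p ≤ 0.40 for Day 28 ORR, 1-sided alpha 0.025. It is met when the exact 95% CI lower limit in the efficacy evaluable population is at least 40% at the number actually enrolled (37 responders if n = 70). All other analyses are descriptive.*
3. In Protocol 9.2 and 9.6 and SAP 3.2 and 9, make the count of 37, and the power and type I error that go with it, explicitly conditional on n = 70.

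The CI should govern and the count should follow from it; writing the two as interchangeable would bring the conflict back at 71. With the stop in place, the CI criterion keeps the type I error between 0.0139 (n = 71) and 0.0199 (n = 68) over this range.

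The cost is text in named sections, with no change to conduct. The headline probability becomes slightly less favourable, the success count rises above 37 with 71 or more enrolled (to 38 at 71 and 72), and the sponsor commits openly to one evaluated hypothesis.
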